5.1 Cost

Cost data will not be collected in the study. As these data often vary by site and insurer, representative unit cost estimates for each healthcare service/medication identified during the collection of outcome measures will be identified. Total costs of care for each study subject will then be estimated by multiplying utilization of healthcare services collected via the CRF by the corresponding unit costs; mean/median total costs of care during the pre- and post-periods will then be estimated and compared. The approach to the pre-post comparison and unit costs will be defined in the SAP.

5.2 Handling of missing data

The SAP will define how missing values and information from subjects lost to follow-up will be handled. Site procedures will be developed to minimize the amount of missing data however, as this is a pragmatic trial, missing data is expected. Certain outcomes are based on data availability from sites (e.g. laboratory values will be summarized for subjects who had data collected).

The extent of missing values will be examined to assess completeness of data among the study cohort. In addition, the characteristics of participants with and without missing data will be examined to assess whether participant characteristics have any relationship to incompleteness.

5.3 Sample size and sample size considerations

Hospital admission rate, which is correlated to total hospital time for the study population, was largely unknown for purposes of sample size estimation. The final enrollment to support hypothesis testing for a primary outcome of total admitted hospital days was initially calculated as 322 subjects (161 subjects in each period). The sample size was evaluated after a planned interim analysis of pre-period data once 75 subjects were enrolled in the pre-period. Based on results of the interim analysis, an adjustment was made at the time of the analysis to revise the primary outcome from total admitted hospital days to hospital admission rate at initial episode of care. The initially estimated final enrollment of 322 subjects, including adjustments for attrition, would support one-sided hypothesis testing (two-sample Pearson chi-square test for proportion difference with equal group weights using a normal approximation) with a significance level of 0.05 and at least 80% power assuming hospital admission rate comparing the pre- and post-periods were 38% versus 23%.

5.4 Data monitoring and quality control

Before any subject enters the study, a representative of the sponsor or CRO will meet with the investigator and core study team to review the procedures to be followed during the study. Electronic data capture (EDC) functionality training will be provided via computer to investigators and authorized designees on recording the data in the CRFs using the EDC system. All subject information and data will be considered private health information and kept confidential in compliance with HIPAA (Health Insurance Portability and Accountability Act of 1996). After the first subject is enrolled, the CRO representative will periodically monitor the progress of the study by conducting on-site visits. The CRO representative will review query statuses remotely, possibly warranting more frequent communication and/or site visits with the investigator and the study site staff. The investigator will make available to the CRO representative source documents (written notes and electronic medical records, if used), signed consent forms, and all other study-related

documents. The investigator and the study site staff will be responsible for data entry of subject data into the CRFs via the EDC system, resolving data queries generated via the EDC system and providing missing or corrected data. The investigator or CRO representative will be responsible for approving all data entry and all changes performed on the data, and endorsing the subject data within the EDC system.

Quality control will be implemented and maintained throughout the conduct of the study. Data collection will involve the use of the EDC system provided by the CRO, to which only authorized personnel will have access. Subject's data will be entered into the EDC system by the investigator or designee using their assigned EDC user account as specified in Section 4.2 Data collection.

6 Study sites and study administrative structure

This study will be performed at approximately 8 study centers in North America.

6.1 Core study team

The core study team for each site will consist of primary investigators, CRO representatives, and sponsor representatives. The core study team will be responsible for training of the site study teams, responsible for adherence to the protocol, monitoring and reporting as consistent with regulation and law, and coordinating and participating in training sessions for the site study teams. The core study team is responsible for coordinating training of the site study teams for both protocol adherence and implementation and operationalization of the new critical pathway, including site-specific considerations. Training will occur before enrollment in the pre- and post-periods for adherence to the protocol. Training will additionally occur for implementation of the new critical pathway during the 2-4 weeks after the last subject is enrolled during the pre-period of the study.

6.2 Site study team

The site study team at each site will consist of the primary site investigators and study administrators, including hospital staff (including physicians, nurses, and/or pharmacists), who will be responsible for adhering to the protocol for both the pre- and post-periods. The site study team will be further supported by the core study team, specifically, the CRO. The site study team will be responsible for participating in training sessions and/or engagement in communication from the core study team, in regards to study background/rationale, site procedures to identify and enroll subjects who are eligible for the study during the pre- and post-periods, data collection, and follow-up of subjects. Specifically, for the post-period, training on the implementation of the new critical pathway is vital. Training will include site procedures, such as how to obtain study drug during the post-period from the hospital pharmacy and the location to administer study drug. This will ensure adherence to the protocol and that operationalization of the study is consistent during both study periods.

7 Ethical considerations

7.1 Regulatory and ethical compliance and protection of human subjects

To ensure safety of participating subjects, this study will be conducted in compliance with the protocol, the rules and regulations of each institutional review board (IRB), informed consent regulations, and standard operating procedures (SOP) at CRO, sponsor, and each study site. This study will adhere to all applicable local regulatory requirements and be governed according to local laws and regulations. The following rules, regulations, and practices will be adhered to: Good Clinical Practice (GCP) guidelines, International Conference on Harmonisation (ICH) Guidelines, Declaration of Helsinki, and the Belmont Report.

7.2 Subject confidentiality

All necessary measures will take place to ensure subject confidentiality. Only site study team members and an independent unit of the CRO will know the identity of participating subjects, however no identifying information will be collected on any study-related documents. Contact information for the subject after their consent will be sent to an independent unit of the CRO, where it will be kept confidential, and will only be used to contact the patient for pre-determined study visits. Any data provided to CRO or sponsor will be de-identified by using the unique subject ID. Neither CRO nor sponsor will have access to any subject identification log. Any data reported or published will be presented as aggregated data, and no individual data will be reported to reduce any risk of subject identification.

7.3 Informed consent procedures

Patients, after being given an explanation of the study, will give voluntary and written informed consent and HIPAA (Health Insurance Portability and Accountability Act of 1996) authorization (in compliance with 21 CFR, Parts 50 and 312) or other appropriate documentation, according to local regulatory requirements, before participating in any study-related procedures.

Informed consent will be obtained from each subject prior to the beginning of any study-specific activities, and will include consent to collection of clinical, economic and humanistic outcomes. This may involve gathering data through chart review or directly eliciting information from subjects. Informed consent during the post-period, or interventional period, will involve consent to treatment through a new critical pathway. Each eligible subject will have the opportunity to read and review the approved informed consent form (ICF) and have the opportunity to ask questions to the participating Study Investigator, Study Coordinator, or other study team member. Signed copies of the ICF and the HIPAA or other locally applicable form will be given to the subject, and both documents will be placed in the investigator's study files.

The participating subject may withdraw participation and/or informed consent at any time throughout the conduct of the study. Withdrawing participation or consent will relieve the subject from any future data collection time points.

7.4 Responsibilities of the investigator and IRB

The responsibilities of investigators include creation of and maintenance of a core study team (Please refer to Section 7 for more information), adhering to protocol requirements, including educational requirements for implementation of the intervention in the post-period, and ultimately, are the institutional leads to support protocol implementation. The study team will be responsible for timely reporting, where appropriate, to the institutional IRB. The investigators must demonstrate reasonable efforts to obtain qualified patients for the study.

The responsibilities of the IRB include adhering to institutional requirements, performing an objective review of the acceptability of the study protocol and analysis plan (i.e. research) in terms of institutional requirements, commitments, regulations, applicable law, and professional conduct and practice, provide continued monitoring and review of research, review of key events (protocol amendments, protocol deviations, adverse events, or non-compliance), review of any required progress reports, and to report any required information to appropriate authorities and/or organizations.

7.5 Publication

All data generated in this study are the property of the sponsor. An integrated clinical and statistical analysis report will be prepared at the completion of the study.

Publication of the results by the investigator will be subject to mutual agreement between the investigator and the sponsor and will follow the sponsor's SOP on publications.

8 Protocol deviations and violations

A *protocol deviation* is any change, divergence, or departure from the study design or procedures that is under the investigator's responsibility and oversight (as defined by regulations) without prior written IRB approval or favorable opinion of an appropriate amendment and that does not have a major impact on the subject's rights, safety, or well-being, or on the integrity and authenticity of the study data. Deviations may include, but are not limited to, departure from inclusion/exclusion criteria, dosing, duration of treatment, failure to perform the required assessments at specified time points, scheduling of visits not in accordance with specifications, or subject safety. Deviating from the protocol is permitted only if absolutely necessary for the safety or clinical management of the subjects and will immediately be reported to the sponsor. Protocol deviations will be reported to the sponsor either verbally or electronically within 5 working days from the day of discovery.

A *protocol violation* is a form of protocol deviation that has a major impact on the subject's rights, safety, or well-being, or on the integrity and authenticity of the study data. Protocol violations will be reported to the sponsor within 24 hours, if possible. The IRB will be notified within the time period dictated by the IRB associated with this study.

10.1 Measurement of lesion characteristics

Measurements are to be taken while the infected area is in a nondependent position, e.g., if infection was on the leg, the subject was lying down, not sitting or standing. All types of infections are to be measured as measurement of erythema upon enrollment and any subsequent physical follow-up visits. Maximal dimensions of erythema, both width and length, are to be recorded in centimeters. Investigators should attempt to find the infection edge that best distinguished erythema from non-erythematous skin. Erythema is to be measured in the dimension of maximal length. The maximal width is to be measured perpendicular to the axis of the maximal length. The maximal width measurement does not have to be in the center if the area of erythema is irregular. The length of the infection is to be multiplied by perpendicular width of wound.

1.0 Introduction

This statistical analysis plan (SAP) outlines the planned analysis for data collected within Allergan study CMO-US-ID-0476, entitled “A Pragmatic Trial Designed to Evaluate a New Critical Pathway for Treatment of Patients with Acute Bacterial Skin and Skin Structure Infections”. This SAP applies to the protocol, Amendment Version 3.0, dated January 11th, 2018, and provides a description of methods for handling the data. The protocol, Amendment Version 3.0, reflects an adjustment to the primary outcome based on the results from the interim analysis.

This pragmatic trial has been developed to assess a new critical pathway for the treatment of ABSSSI; it will include the use of guideline-based criteria to identify patients eligible for outpatient parenteral antibiotic therapy (OPAT), and, for those who meet these criteria, the use of dalbavancin — a novel, single-dose, long-acting, second generation lipoglycopeptide indicated for the treatment of ABSSSI caused by susceptible strains of Gram-positive bacteria.

2.0 Study Objectives

2.1 Primary Objective

The primary objective of the study is to estimate the difference in hospital admission rate at the initial episode of care comparing ABSSSI patients receiving care before implementation of the new critical pathway and after implementation.

2.2 Secondary Objectives

The secondary objectives of this study are to estimate the difference in the following outcomes during initial care (the date of enrollment to 14 days) and follow-up (30 days after initial care) comparing ABSSSI patients receiving care before implementation of the new critical pathway and after implementation:

- Total admitted hospital days during initial care and follow-up
- Infection-related total admitted hospital days during initial care and follow-up
- ED length of stay (LOS) at initial episode of care (time from triage to release from ED)
- Infection-related major surgical interventions that required operating room time during initial care and follow-up (number of expected major surgeries, number of unexpected major surgeries, and total number of major surgeries)
- Infection-related hospitalizations during initial care and follow-up
- Infection-related hospitalizations during initial care and follow-up that resulted in admission to Intensive Care Unit (ICU)

- All cause hospitalizations in the 30 days post discharge from the hospital or release from the ED
- Infection-related ED visits during initial care and follow-up (number of expected, number of unexpected and number of total ED visits during initial care and follow-up)
- Infection-related outpatient healthcare visits (e.g., physicians' office visits, ED visits, infusion center visits, home health visits) during initial care and follow-up (number of expected visits, number of unexpected and total number of visits)
- Use of a PICC line or central line to administer antibiotic therapy during initial care and follow-up (number of patients who have a PICC or central line placed)
- Infection-related healthcare visits (e.g., hospitalizations, ED visits, other outpatient visits) due to PICC line or central line used to administer antibiotic therapy during initial care and follow-up (number of expected visits, unexpected visits and number of total visits)
- Serious adverse events (SAEs) during initial care and follow-up
- Patient satisfaction with care (patient reported or completed by a caregiver if the patient cannot complete)
- Patient work and productivity loss (patient reported or completed by a caregiver if the patient cannot complete)
- Patient Health-related Quality of Life (HRQoL) (patient reported or completed by a caregiver if the patient cannot complete)

3.0 Study Design

This study will employ a "pre-post" pragmatic design, which will consist of both a pre-period, or an observational baseline period, and a post-period, or an interventional period. The pre-period and post-period will consist of independent groups of patients. During the pre-period, each participating site will implement the first component of the critical pathway through implementation of guideline-based criteria to identify patients at the point of care in the ED, obtain informed consent, and monitor enrolled patients. Sites will initiate treatment for ABSSSI with "usual care," defined as site- or physician-specific antibiotic treatment of ABSSSI with coverage for a known or suspected Gram-positive infection (e.g., vancomycin, linezolid, and daptomycin) to each study patient who meets all inclusion and exclusion criteria. Blinding of treating physician to patient enrollment in the study during the pre-period will ensure unbiased provision of usual care. During the post-period, for all patients who provide informed consent and are subsequently enrolled, each participating site will additionally implement the second component of the new critical pathway, use of dalbavancin, at the point of care in the ED to each study patient who meets all inclusion and exclusion criteria. Sites are expected to transition to the post-period at the enrollment of 50 patients. There is no expectation for all sites to transition to the post-period at the same time.

For both periods of interest, patient follow-up spans the period beginning on the day of study enrollment and ends 44 days thereafter, which incorporates an initial care period of 14 days (reflecting the 10–14-day period during which most antibiotics are anticipated to be required for care of ABSSSI) and a subsequent “follow-up” period of 30 days. Study measures will be collected as described in the protocol and will be based on medical records, unless otherwise indicated.

A schedule of assessments is provided in Appendix A. Follow-up visits will be scheduled for approximately 24 hours after enrollment (post-period only), 48–72 hours after enrollment (post-period only), 14 days after enrollment (both periods), and 44 days after enrollment (both periods). Any additional visits to the visit schedule below will be at the discretion of the patient and treating physician.

The duration of the study was not predetermined; it is dependent on the time required to enroll the necessary number of eligible patients (161 patients per time period; 322 patients enrolled in all).

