- Known or suspected infections that are severe, life-threatening, or are not included in the ABSSSI FDA guidance¹, including the following examples:
 - [REDACTED]
 - [REDACTED]
 - [REDACTED]
 - [REDACTED]
 - [REDACTED]
- [REDACTED]
 - [REDACTED]
 - [REDACTED]
 - [REDACTED]
 - [REDACTED]
 - [REDACTED]
 - [REDACTED]
 - [REDACTED]
 - [REDACTED]
- [REDACTED]
 - [REDACTED]

	
[REDACTED]
 
 ■ [REDACTED] ■ [REDACTED] ■ [REDACTED] ■ [REDACTED] 
 • Severe neurological disorder leading to severe immobility or confined to wheelchair or bed (e.g. paraplegia and hemiplegia) • Bilateral lower extremity involvement of the suspected infection (to exclude patients with chronic venous stasis) • Unwilling or unable to follow study procedures
Intervention	The new critical pathway under study is defined as (1) use of guideline-based patient identification criteria, and, for those who meet these criteria, (2) use of dalbavancin, a long-acting antibiotic with an abbreviated administration schedule.
Comparator treatment	Usual care (i.e. investigator choice antimicrobial therapy for a suspected or known Gram-positive infection of susceptible organisms)
Study design	Pre-period versus post-period trial
Study duration and sample size	The duration of the study will not be predetermined, but rather will depend on the number of included sites and eligible subjects at each site. Both the pre- and post-periods will run until approximately 322 subjects are enrolled, or 161 subjects per period. Section 6.3, Sample size, provides information on the minimum number of subjects.
Sites	This study will be performed at approximately 8 US study centers.
Baseline characterization	
 • Study site characteristics where subject was enrolled • Demographics • Comorbidities

	
 • Charlson Comorbidity Index • Infection type 
 ○ Cellulitis/erysipelas, ○ Wound infection, or ○ Major cutaneous abscess • Infection characteristics • Healthcare utilization in prior three months

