2.1.2 Rationale of study design

The design of this study allows for a site to understand baseline treatment patterns for ABSSSI, then after this period, to implement an institution-level intervention (i.e., each site contributes study subjects to both treatment arms), as opposed to concurrently across sites (i.e., each site contributes study subjects to a single arm). Use of this design removes site-level variables as a source of potential confounding and enables comparisons of the new critical pathway to usual care in the same setting(s) and similar subject populations.

[figure not shown]
The study is designed in a “pragmatic” fashion (i.e., minimal inclusion/exclusion criteria, which will enable an examination of the impact of the new critical pathway under “real-world” conditions, with good generalizability/applicability to clinical practice.

[figure not shown]
In order to account for temporal trends, sites will also be required to generate data, or reports, on admission rates during the pre- and post-period for other infections, including diabetic foot infections (currently part of exclusion criteria) and pneumonia (a non-skin infection). This will aid in supporting a true difference in outcomes during the pre-period versus the post-period based on the new critical pathway for ABSSSI.

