4.10 Potential Hy's Law cases

Every subject that meets potential Hy's law criteria,

- ALT or AST $\geq 3 \times \text{ULN}$ AND
- Total Bilirubin $\geq 2 \times \text{ULN}$ AND
- Alkaline Phosphatase $< 2 \times \text{ULN}$

occurring anytime from the time he or she signs the ICF for the trial until the final follow up visit, investigators will notify the sponsor immediately when all the above criteria have been met. A potential Hy's law case will be sent directly to the sponsor by emailing [contact] on an AE of Special Interest Form along with the SAE Report Form as soon as possible (within 24 hours of learning of the potential Hy's law). The CRF for potential Hy's law cases will be completed within seven calendar days. Every effort to determine the cause of the liver enzyme abnormalities will be made, and close monitoring will be initiated in conjunction with the medical monitor and in accordance with the FDA "Guidance for Industry: Drug Induced Liver Injury- Pre-Marketing Clinical Evaluation" July 2009.

5 Data analysis

Frequency and proportion of subjects deemed eligible and ineligible for study enrollment based on each of the inclusion/exclusion criteria will be summarized. The frequency and proportion of subjects who successfully complete the study, withdraw, were lost-to-follow-up, and who terminated the study early, will also be reported. Subject characteristics at baseline will be summarized and described for all enrolled subjects and compared between the pre- and post-periods. Site characteristics will also be described. Descriptive statistics (count, mean, standard deviation, range for quantitative variables, and counts and percentages for categorical variables) will be reported for all outcomes. The difference in study outcomes between the pre- and post-period will be assessed using appropriate statistical methods, accounting for study site, with adequate power. The primary outcome will be tested for simple superiority, and subsequently, tested for non-inferiority with a 10% margin between the pre- and post-periods.

All analyses will be specified in a detailed statistical analysis plan (SAP) that will be prepared subsequently and before database lock. The SAP will include table and figure shells.

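### The 50-patient site transition does not fit 161 patients per period at about 8 sites, and with a primary analysis that ignores site, the claimed removal of site confounding is not secured

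*SAP*

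**What the plan says.** **Transition rule.** SAP 3.0 states: "Sites are expected to transition to the post-period at the enrollment of 50 patients". It adds: "There is no expectation for all sites to transition to the post-period at the same time". The protocol has no 50-patient rule. It ties pathway training to the last pre-period enrolment (2.1 and 6.1).

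**Size.** SAP 3.0 gives "161 patients per time period; 322 patients enrolled in all". The protocol synopsis agrees: "Both the pre- and post-periods will run until approximately 322 subjects are enrolled, or 161 subjects per period". On sites, the synopsis says: "This study will be performed at approximately 8 US study centers".

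**Claim.** Protocol 2.1.2 argues from the fact that "each site contributes study subjects to both treatment arms" and concludes: "Use of this design removes site-level variables as a source of potential confounding".

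**Analysis.** Protocol section 5 promises that differences in outcomes "will be assessed using appropriate statistical methods, accounting for study site, with adequate power". The SAP aggregates data across sites (6.1.1) and tests the primary outcome with a one-sided two-sample Pearson chi-square without stratification. Site is not among the covariates listed for the secondary logistic regression (6.2.6.1). Site enters only through summary rows and optional repeats by site (6.1.7, 6.2.1, 6.2.6.1).

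Neither document gives a per-site post-period target, a site cap, or a rule for a site that has not reached 50 when the pre-period total is met.

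**The concern.** The transition number and the period total cannot both operate as written at about 8 sites. The natural way to run them together is that a fast site crosses at 50 and starts filling the post-period, while the others stay in the pre-period until it closes at 161. Site shares may then differ between the periods.

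Having every site in both periods does not by itself remove site confounding. A pooled comparison is free of it only if site shares match, or if the analysis conditions on site. The plan secures neither. If hospitals differ in how readily they admit these patients, a change in mix moves the pooled admission rate with no pathway effect at all. It could create an apparent benefit or hide a real one.

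**Working it through.** **1. The plan's own power figure.** Inputs (SAP 6.1.2): 38% versus 23%, one-sided α = 0.05, equal groups, normal approximation.

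n = [z₀.₉₅·√(2p̄q̄) + z₀.₈₀·√(p₁q₁ + p₂q₂)]² / δ², with p̄ = 0.305 and δ = 0.15

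= [1.645 × 0.651 + 0.842 × 0.642]² / 0.0225 ≈ 116 per period.

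With 161 per period power is 90.2%. With 145 (10% attrition) it is 87.4%. The stated minimum of 80% reproduces and is not in dispute.

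**2. The 50-patient rule against the totals.**

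- Read per site: 8 × 50 = 400, which is 400/161 ≈ 2.5 times the period target and more than the whole trial (322).
- Sites that can reach 50 within 161: 161/50 = 3.2, so three. They would use 150 and leave 11 for the other five.
- Average per site and period: 161/8 ≈ 20.
- Read trial-wide: 50 is below the 75 pre-period subjects at the interim analysis (SAP 6.1.2) and below 161, so this reading fails as well.
- Read as a ceiling (move at 50, or when the pre-period total is met): this works arithmetically, but it is not written and does not control site shares.

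**3. What an uncontrolled mix could do.** The documents give neither site enrolment speeds nor site admission rates, so everything in this step is assumed. Eight sites, a 3-week (0.69-month) training gap, the ceiling reading, the post-period closing at 161, and no pathway effect. The largest site admits 25% and the others 45% in both periods.

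*Speeds of 10, 4, 2, 1, 1, 1, 0.5 and 0.5 per month.* Site 1 reaches 50 at month 5, when the pre-period stands at 100. The other sites supply the remaining 61 at 10 per month and close it at month 11.1. Site 1 starts its post-period at month 5.69 and has 61 patients by month 11.79, when the others join. The last 100 arrive at 20 per month, half of them at site 1, so it ends with 61 + 50 = 111.

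- Pre: (50 × 0.25 + 111 × 0.45)/161 = 38.8%
- Post: (111 × 0.25 + 50 × 0.45)/161 = 31.2%
- False fall: 7.6 points. The one-sided 5% test would reject about 41% of the time.

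| Assumed speeds per month | Site 1 pre | Site 1 post | Pooled pre | Pooled post | False fall |
|---|---|---|---|---|---|
| 10, 4, 2, 1, 1, 1, 0.5, 0.5 | 50/161 | 111/161 | 38.8% | 31.2% | 7.6 points |
| 8, 5, 2, 1, 1, 1, 1, 1 | 50/161 | about 79/161 | 38.8% | 35.2% | 3.6 points |
| 6, 4, 3, 2, 1.5, 1.5, 1, 1 | 30% | 30% | 39.0% | 39.0% | 0 |

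In the second case the test rejects about 16% of the time. In the third, no site reaches 50 before closure. If the admission rates are swapped (largest site 45%, others 25%), the first case becomes a false rise of 7.6 points.

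**4. What stratification does.** In all three cases the difference within each site is 0 (25% − 25%, 45% − 45%), so a site-stratified risk difference is exactly 0. The cost is some precision. Mantel-Haenszel weights are n₁n₀/(n₁ + n₀). In the first case the weight is 50 × 111/161 = 34.5 for site 1 and, because the other seven keep the same ratio, 111 × 50/161 = 34.5 for them together. The total of 69 compares with 161 × 161/322 = 80.5 under equal shares. That is worth about 138 patients per period, for which the formula in step 1 gives power of roughly 86% before attrition.

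**The case against.** The best defence is that 50 is only an expectation. Read as a ceiling inside a study-wide total of 161, it contradicts nothing, because not every site need reach it. That stands in part: the ceiling reading is workable. But the SAP does not state it, and it leaves site shares free to differ.

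A reader might go further and infer three things that the documents do not support.

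- *That the primary result will be biased towards the pathway.* Site counts and rates are not given, one plausible enrolment pattern gives no bias, and the sign depends on which sites admit more.
- *That some sites will have patients in one period only.* Nothing rules this out, but nothing plans it. Protocol 2.1.2 expects each site in both periods, and every site in the illustration has both.
- *That only a change to the enrolment rule can cure this.* Where every site has both periods, a site-stratified analysis removes the bias from site mix completely. Restricting the pooled test to sites with both periods would remove none of the 7.6 points. Capping site 1 after the fact at its pre-period count would discard 111 − 50 = 61 of 161 post-period patients (38%).

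Timing also counts against relying on quotas. SAP version 1.0 is dated February 2019, more than a year after the January 2018 protocol amendment that already reflected the interim analysis, so enrolment may be well advanced.

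**Conclusion.** The concern holds in limited form. On the documents' own numbers, 50 per site does not fit 161 per period at about 8 sites, and no rule keeps a site's share similar in the two periods. Since the planned primary analysis ignores site, the Protocol 2.1.2 claim is an assumption and not a property of the design.

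The size is not identified. Under the assumptions in the working, the bias runs from 0 to about 8 points, up to half of the planned 15, in either direction. This should be corrected before the analysis. It is not fatal: the power statement is unaffected, and the main remedy lies in the analysis and is already promised in Protocol section 5.

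**What to change.** 1. **Reconcile the trigger.** State in SAP 3.0 and in the protocol how 50 relates to 161 per period, for example as a per-site ceiling, with remaining sites moving when the pre-period total is met.
2. **Balance site shares where still possible.** At sites still enrolling, set the post-period target near the pre-period count. Do not discard patients already enrolled.
3. **Stratify the primary comparison by site**, for example with a Cochran-Mantel-Haenszel test and risk difference, and put site in the logistic model regardless of stepwise selection.
4. **Report enrolment and the primary outcome by site and period.** Much of this is already planned in SAP 6.2.1 and 6.2.6.1. State that a site with one period only contributes nothing to the stratified estimate.
5. **Limit the Protocol 2.1.2 claim** to the site-adjusted comparison.

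Cost: wording changes, a site target in the enrolment system where it still applies, slower closure at slow sites, and some loss of precision from sparse or unbalanced sites. The planned total of 322 does not change.
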